6.10 Dietary Counseling

Dietary counseling will be provided to all study subjects in accordance with dietary recommendations for CKD patients (e.g., [KDIGO 2013](#)) at the time points indicated in the Schedule of Events (see Appendix 1). In addition, if a subject requires treatment for sustained, clinically-significant worsening of metabolic acidosis during the study in the judgment of the Investigator, diet counseling (i.e., reduced protein intake, vegetarian/vegan protein sources) may be implemented as clinically appropriate and in agreement with the Medical Monitor.

6.11 Adverse Events

6.11.1 *Definition of an Adverse Event*

An AE is defined as: “Any untoward medical occurrence in a patient or clinical investigation subject administered a pharmaceutical product and which does not necessarily have a causal relationship with this treatment” (*ICH E2A Guideline: Clinical Safety Data Management: Definitions and Standards for Expedited Reporting*, October 1994). An AE can therefore be any unfavorable or unintended sign (including a clinically significant abnormal laboratory finding), symptom, or disease temporally associated with the use of a medicinal

(investigational) product, whether or not related to the medicinal (investigational) product. This includes:

- Any new medical condition, sign or symptom or newly diagnosed event that occurs during the AE reporting period, including signs or symptoms associated with an underlying condition that were not present prior to the AE reporting period (from the time the subject signs the ICF until the completion of the last study visit assessments);
- A previous condition that has worsened in severity or frequency or changed in character during the AE reporting period;
- Complications that occur as a result of protocol-mandated interventions;
- Signs, symptoms or the clinical sequelae of a suspected drug interaction; and
- Signs, symptoms or the clinical sequelae of a suspected overdose of either investigational product or a concomitant medication.

For the purposes of this protocol, events that are not considered AEs include:

- Isolated decline in blood bicarbonate or blood pH, even if assessed as clinically significant by the Investigator;
- Anticipated fluctuations of pre-existing disease(s) or condition(s) present or detected at the start of the study unless judged by the Investigator to be more severe than expected for the subject's underlying condition;
- Diagnostic and therapeutic non-invasive and invasive procedures, such as surgery, should not be reported as AEs. However, the medical condition for which the procedure was performed should be reported if it meets the definition of an AE. For example, an acute appendicitis that begins during the AE reporting period should be reported as the AE and the resulting appendectomy should be recorded as treatment of the AE;
- Placement of a dialysis access
 - If the access placement was prompted by clinically significant renal function decline during the study, then the latter should be reported as an AE and the access placement should be reported as an action taken for the AE.
- Overdose in the absence of other signs/symptoms will not be reported as an AE in its own right; and
- Pregnancy; however, any pregnancy complication should be recorded as an AE.

Out of range laboratory results and abnormal ECGs, vital signs and other safety assessments will be considered AEs if they meet at least one of the following criteria:

- Associated with symptoms or lead to a diagnosis (in such case the symptom or diagnosis should be recorded as an AE);
- Lead to discontinuation of study drug; or

- The abnormality is deemed clinically significant in its own right (i.e., if some action or intervention or alteration of treatment is required or if the Investigator judges the change to be beyond the range of normal physiological fluctuation).

6.11.2 Definition of a Serious Adverse Event

A serious adverse event (SAE) is an untoward medical occurrence that at any dose:

- Results in death.
- Is life-threatening. (This refers to a subject who, in the view of the Investigator or Tricida, was at risk of death at the time of the event; it does not refer to an event that hypothetically might have caused death if it had been more severe).
- Requires inpatient hospitalization or prolongation of existing hospitalization, with the exception of:
 - Visits to the emergency room or hospital department that do not result in a hospital admission lasting more than 24 hours
 - Elective surgery for a pre-existing condition that has not worsened
 - Routine health assessments requiring admission not associated with any deterioration in condition
 - Social admission (lack of housing, family circumstances, etc.)
- Results in persistent or significant disability/incapacity.
- Is a congenital anomaly or birth defect.
- Is an important medical event that may not be immediately life-threatening or result in death or hospitalization but may jeopardize the subject or may require medical or surgical intervention to prevent one of the outcomes above (e.g., blood dyscrasias, convulsions).

Either the Investigator or Tricida can determine that an AE meets the definition of serious. If either believes that the event is serious, the event must be considered serious and evaluated by Tricida for expedited reporting.

6.11.3 Definition of a Suspected Adverse Reaction

A suspected adverse reaction is an AE for which there is a reasonable possibility that the drug caused the AE. For the purposes of Investigational New Drug (IND) safety reporting, “reasonable possibility” means there is evidence to suggest a causal relationship between the drug and the AE.

All AEs judged by either the Investigator or Tricida as having a reasonable causal relationship to a study drug will be designated as suspected adverse drug reactions.

6.11.4 Procedures for Eliciting, Recording and Reporting Adverse Events

6.11.4.1 Adverse Event Reporting Period

AEs, including SAEs, will be collected throughout the study period, beginning from the time the subject signs the ICF until the subject's last study visit. Any AE or SAE that is assessed by either the Investigator or Tricida as related to the investigational drug and is ongoing at the last study visit will be followed, whenever possible, until it resolves or becomes stable or the subject is lost to follow-up.

All subjects who have been exposed to investigational product will be evaluated for AEs. Treatment-emergent adverse events (TEAEs) are defined as those that occur on or after the date of the first dose of investigational product. Non-treatment emergent adverse events (e.g., events occurring during Screening) should be recorded as medical history unless related to a study procedure, in which case, they should be recorded as adverse events.

6.11.4.2 Eliciting Adverse Events

Information on AEs and SAEs will be elicited at each AE assessment time point specified in the Schedule of Events (Appendix 1) by asking the subject an open-ended question such as: "Since you were last asked, have you felt unwell or different from usual in any way?" The subject may report AEs spontaneously at any time.

6.11.4.3 Assessing Adverse Events

The Investigator should follow the guidelines for rating severity of adverse events:

Severity	Definition
Mild	Awareness of signs or symptoms, but easily tolerated; no disruption of normal activities; symptoms are transient and would not require medication or medical evaluation
Moderate	Discomfort enough to cause interference with usual activities and treatment may be required
Severe	Incapacitating with inability to do work or do usual activities; may require medical evaluation and/or treatment; the investigational product may have been discontinued

It is important to note the distinctions between severe AEs and serious AEs. Severity is a classification of intensity of a specific event, whereas an SAE is an AE that meets any of the regulatory specified criteria required for designation as seriousness described in [Section 6.11.2](#) (e.g., a headache may be severe [interferes significantly with subject's usual function] but would not be classified as serious unless it met one of the criteria for SAEs).

The Investigator will assess relationship of the AE to the investigational drug, TRC101, using the following definitions. A suspected relationship (related, probably, possibly)

between the events and the study drug means, in general, that there are facts (evidence) or arguments to suggest a causal relationship. If the relationship to the study drug is considered to be unlikely or not related, an alternative suspected etiology should be provided if available (e.g., concomitant medications, intercurrent illness/events).

Relationship	Definition	Example
Related	Causal relationship is certain	The temporal relationship between drug exposure and the AE onset/course is reasonable, there is a clinically compatible response to de-challenge, other causes have been eliminated; the event must be definitive pharmacologically or phenomenologically, using a satisfactory rechallenge procedure if necessary.
Probable	High degree of certainty for causal relationship	The temporal relationship between drug exposure and AE onset/course is reasonable, there is a clinically compatible response to dechallenge (re-challenge is not required), unlikely to be attributed to disease or other drugs.
Possible	Not reasonably related although a causal relationship cannot be ruled out	The temporal relationship between drug exposure and the AE onset/course is reasonable or unknown, de-challenge information is either unknown or equivocal, could also be explained by disease or other drugs.
Unlikely	Not reasonably related although a causal relationship cannot be ruled out	Disease or other drugs provide plausible explanation.
Unrelated	No possible relationship	The temporal relationship between drug exposure and the AE onset/course is unreasonable or incompatible, or a causal relationship to study drug is impossible.

The Investigator will use the following categories to assess the outcome of each AE:

- Recovered/resolved;
- Not recovered/ not resolved;
- Recovered/resolved with sequelae;
- Fatal; or
- Unknown.

“Fatal” should be recorded as an outcome when the AE results in death. If more than one AE is possibly related to the subject's death, the outcome of death should be indicated for the AE

that, in the opinion of the Investigator, is the most plausible cause of death. All other ongoing AE/SAEs will be recorded as not recovered/not resolved at the time of death.

Although “fatal” is usually an outcome of an event, events such as sudden death or unexplained death should be reported as SAEs.

The action taken with regard to study drug in response to each AE will be assessed by the Investigator using the following categories:

- No action taken;
- Study drug interrupted;
- Study drug discontinued; or
- Not applicable (e.g., subject was not receiving study drug at the time of the AE).

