10.1.15 Treatment-Emergent Adverse Events

Treatment-emergent adverse events (TEAEs) are defined as all AEs that begin on or after the time of the first dose of study drug (also see Section 11.4.1). Related AEs are those reported by investigators as possibly related, probably related, or related to study drug.

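### The causality grades Possible and Unlikely share one definition, which contradicts the protocol's other rules for Possible, and the SAP's related/not-related cut falls between them

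*Protocol*

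**What the plan says.** Protocol 6.11.4.3 tells the investigator to assess relationship to study drug by a table with three columns: the grade, its Definition and an Example. The grades run from Related through Probable, Possible and Unlikely to Unrelated. The Definition for both *Possible* and *Unlikely* is "Not reasonably related although a causal relationship cannot be ruled out".

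The Examples differ. For *Possible*, timing is reasonable or unknown, and "de-challenge information is either unknown or equivocal, could also be explained by disease or other drugs". For *Unlikely* the whole entry is "Disease or other drugs provide plausible explanation".

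The paragraph above the table groups the grades. It begins "A suspected relationship (related, probably, possibly" and explains the group as meaning, in general, "that there are facts (evidence) or arguments to suggest a causal relationship". On the other side, "If the relationship to the study drug is considered to be unlikely or not related, an alternative suspected etiology should be provided if available".

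Protocol 6.11.3 states: "A suspected adverse reaction is an AE for which there is a reasonable possibility that the drug caused the AE". It lets either the investigator or the sponsor make that designation.

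SAP 10.1.15 states: "Related AEs are those reported by investigators as possibly related, probably related, or related to study drug". SAP 11.4.1 repeats the rule, and SAP 15.2 lists a summary of study-drug-related TEAEs.

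**The concern.** Two adjacent grades have the same definition, and the analysis splits the scale between them. An investigator who goes by the Definition column has no basis for choosing one over the other. The shared wording also fits only one of the two grades: it denies a reasonable relationship, while the rest of the protocol puts *Possible* on the suspected side.

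Two things depend on the choice. One is whether a TEAE enters the related-TEAE summary. The other is follow-up: under Protocol 6.11.4.1, AEs still ongoing at the last visit are followed to resolution or stability if the investigator or the sponsor assessed them as related. SAP 11.6 reports 37 centres that randomized subjects, so many investigators would have worked from this table.

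**Working it through.** No calculation applies and the plan gives no figure to reproduce. The check sets the texts side by side.

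| Source | Possible | Unlikely |
|---|---|---|
| Protocol 6.11.4.3, Definition | "Not reasonably related although a causal relationship cannot be ruled out" | identical |
| Protocol 6.11.4.3, Example | timing and de-challenge conditions; other causes could also account for the event | other causes plausibly account for the event; no timing or de-challenge condition |
| Protocol 6.11.4.3, paragraph above the table | suspected relationship | not suspected; alternative cause requested |
| SAP 10.1.15 and 11.4.1 | related | not related |

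1. **Duplication.** The two Definition entries agree word for word. Even if the source table held one merged cell, the two grades would still share one definition.

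2. **Contradiction for *Possible*.** The Definition says the event is not reasonably related. The paragraph above says facts or arguments suggest causation. Section 6.11.3 requires a reasonable possibility. Read literally, an AE graded *Possible* is related in the SAP yet fails the test for a suspected reaction. There is no such conflict for *Unlikely*, so the wording belongs to that grade.

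3. **Whether the Examples settle it.** Only partly. An event that another cause could explain, with reasonable timing and unknown de-challenge, meets the *Possible* example. If the other cause is also plausible, it meets the *Unlikely* example as well. Diarrhoea in a patient with CKD on several medicines could meet both.

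4. **Where the SAP cuts.** The cut follows the grouping in the protocol paragraph, so the SAP agrees with that text. It falls exactly where the Definition column makes no distinction.

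5. **Missing grades.** SAP 11.2 imputes a missing relationship as possibly related. Missing values therefore count as related, under a grade whose definition denies a reasonable relationship.

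6. **Expedited reporting.** Protocol 6.11.6 requires every SAE, including those in the Follow-up Period, to be reported within 24 hours whatever its grade. Under 6.11.6.1 the sponsor makes its own suspected-reaction determination for each serious event. The investigator's view still counts as one of the two routes in 6.11.3. It also matters for SAEs learned of after the Follow-up Period, which are reportable only if relatedness is a reasonable possibility.

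7. **Follow-up of ongoing AEs.** Section 6.11.4.1 makes this depend on relatedness without saying which grades qualify. Section 6.11.6 separately requires all SAEs to be followed until resolved or stable, so the exposure is mainly in non-serious AEs.

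**The case against.** The strongest reply is that the boundary exists. The paragraph above the table puts *Possible* on the suspected side and *Unlikely* on the other, the Examples differ, and the SAP cut matches that grouping. This stands: a reader might infer that the split is undefined, and the documents do not support that. They support an inconsistent definition, with one column contradicting the surrounding text.

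A reader might also infer that the grade decides whether a serious event gets expedited review. It does not, for the reasons in step 6: an *Unlikely* grade alone cannot remove a reported SAE from the sponsor's assessment.

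Nor should the related-TEAE summary be read as a main safety result. The protocol's safety endpoints are AEs, SAEs, withdrawal of treatment due to AE, and the confirmed high-bicarbonate criterion. Related TEAEs form one of six summaries listed in SAP 15.2, and the other five do not use the cut. Investigators grade blinded, so the ambiguity applies in both arms.

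Finally, it is tempting to take a size from TRCA-101, where related TEAEs occurred in 26.9% of 104 TRC101 subjects (0.269 × 104 ≈ 28) and 12.9% of 31 placebo subjects (0.129 × 31 ≈ 4). Those are the entire related incidences in a different, two-week study. Neither its causality scale nor its share of *Possible* grades is given, so they do not estimate misclassification here.

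None of this removes the contradiction in the *Possible* definition.

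**Conclusion.** The point holds as a drafting error in an operative table. The Definition of *Possible* is wrong as written, because it conflicts with the paragraph above it and with Section 6.11.3, and it leaves the boundary used by the SAP inconsistently defined. The duplication and the contradiction are certain from the text.

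The consequence is modest: one planned safety summary, and the follow-up of some ongoing AEs. Primary and secondary efficacy analyses are untouched. How many AEs could be graded either way cannot be estimated from the documents. The practical effect assumes that at least some investigators graded by the Definition column; those who relied on the preceding paragraph would have been guided to the SAP's grouping.

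**What to change.** In Protocol 6.11.4.3, give *Possible* its own Definition, consistent with 6.11.3 and the preceding paragraph: a causal relationship is a reasonable possibility. Keep the current words for *Unlikely* only, and notify sites.

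For AEs already graded, run a blinded query before database lock, limited to those marked *Possible* or *Unlikely*, asking the investigator to confirm or revise the grade against the corrected definitions. This re-collects some judgements retrospectively, so it is a small site burden and not free.

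In SAP 15.2, state that the relationship summary shows each of the five levels. That section already plans a tabulation by relation to study drug and ranks all five, and Protocol 8.6 commits to TEAEs by causality, so this only makes the layout explicit. It lets a reader see how much of the related total rests on *Possible*.

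The cost is one table cell, a site notice, a limited query round and one SAP sentence. No new procedure or assessment visit is needed.

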5.3 Dosing Regimen

The study drug dose titration algorithm is described in [Appendix 2](#). Dose titrations can only be performed during a clinic visit. If the dose of study drug is changed, the subject will start the new dose at lunch time on the titration day. Dose titrations should be performed on the basis of onsite i-STAT blood bicarbonate measurements only.

The study drug dose will be fixed for the first 4 weeks of the Treatment Period (during this time each subject will receive the study drug dose assigned at randomization [Baseline Visit]); no study drug dose adjustments will be permitted before the Week 4 Visit, except for subjects with elevation of blood bicarbonate ≥ 27 mEq/L. If the blood bicarbonate level is 27 to 30 mEq/L at any time during the Treatment Period through Week 11, the study drug dose will be decreased by 1 packet/day (minimum dose is 0 packets/day). Beginning at the Week 4 Visit, subjects with a blood bicarbonate level below the normal range (< 22 mEq/L) will have a blinded adjustment of the study drug dose in accordance with the titration algorithm (see [Appendix 2](#)). The study drug dose will only be titrated if NO dose changes have been made during the previous 14 days. If blood bicarbonate is confirmed to be > 30 mEq/L at any time during the study, the study drug treatment will be interrupted, no study drug will be dispensed to the subject, and the subject will be invited for a visit in approximately 1 week to retest blood bicarbonate. If blood bicarbonate decreases to < 27 mEq/L and the subject is still within the Treatment Period, study drug should be re-started at a lower dose in accordance with the titration algorithm (see [Appendix 2](#)). If blood bicarbonate is ≥ 27 mEq/L, the study drug dosing should be withheld until blood bicarbonate is < 27 mEq/L.

No dose titration will be allowed after Week 11 (i.e., 77 days after the day of the first dose). Dose titrations are blinded.

The Medical Monitor must be notified within 24 hours of confirmation of a bicarbonate value > 30 mEq/L or < 12 mEq/L. Dose interruptions due to blood bicarbonate elevations should be performed on the basis of i-STAT measurements, except in unusual situations when they may be based on confirmed non-i-STAT blood bicarbonate values > 30 mEq/L, e.g., if i-STAT values cannot be obtained because the subject is hospitalized.

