8.5.3.3 Sensitivity Analyses and Exploratory Efficacy Endpoint Analyses

In order to evaluate the potential effect of missing data on the primary and secondary efficacy results, sensitivity analyses will be performed using multiple imputation models under a MNAR assumption for the MITT analysis set. These analyses will be described in the SAP.

The SAP will also describe the analysis methods for the exploratory efficacy endpoints.

8.6 **Safety Analysis**

Safety will be summarized by treatment group for subjects in the safety analysis set. The number and percentage of subjects with treatment-emergent AEs (TEAEs) classified by system organ class (SOC) and preferred term (PT); number (%) of subjects experiencing TEAEs by severity, causality, seriousness and action taken with regard to study drug will be summarized by treatment group. The number (%) of subjects with TEAEs leading to discontinuation of study treatment will also be summarized by treatment group. Subjects will be counted only once at each SOC and PT level of summary. Clinical laboratory test results, vital signs and ECG findings will be summarized using descriptive statistics by treatment group and time point. Categorical display methods (e.g., frequencies, shift tables) and plots of laboratory values over time may also be used, as appropriate. Worsening or newly observed, clinically significant physical examination findings will be reported as adverse events.

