Appendix 2: Study Drug Titration Algorithm

Blood Bicarbonate (mEq/L)	Before Week 4 Visit	Week 4 through Week 11
< 12*	Evaluate for new acute acidotic process, contact Medical Monitor. Maintain dose pending discussion with Medical Monitor	Evaluate for new acute acidotic process, contact Medical Monitor. Maintain dose pending discussion with Medical Monitor.
12 to < 22	Maintain dose until next scheduled visit.	Increase the study drug dose by 1 packet/day (maximum dose is 3 packets/day). Only increase the dose if NO dose changes have been made during the previous 14 days. Retest blood bicarbonate at next scheduled visit.
22 to < 27	Maintain dose until next scheduled visit.	
27 to 30	Decrease the study drug dose by 1 packet/day (minimum dose is 0 packets/day). Invite subject for a visit in approximately 1 week to retest blood bicarbonate. Only decrease the dose if NO dose changes have been made during the previous 14 days.	
> 30*	Interrupt (hold) study drug. Invite subject for a visit in approximately 1 week to retest blood bicarbonate. If blood bicarbonate at that visit is: 
• < 27 mEq/L, restart study drug at a lower dose (1 packet/day less than before dose interruption).• ≥ 27 mEq/L, continue to hold the dose and retest again in approximately 1 week.	

* Blood bicarbonate value of < 12 mEq/L or > 30 mEq/L must be confirmed by a repeated measurement from a separate blood draw.

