15.2 Adverse Events

TEAEs are defined in Section 11.4.1. All reported AEs (including non-TEAEs) will be listed. All TEAE summary tables will present the number and percentages of subjects reporting TEAEs. A summary of TEAEs by severity, seriousness, and relation to study drug will be tabulated. In addition, TEAEs will be summarized by MedDRA system organ class and preferred term. Subjects can have more than one TEAE per system organ class and preferred term. These summaries will include the following:

- All TEAEs
- TEAEs by worst severity
- Study drug related TEAEs
- Serious TEAEs
- TEAEs leading to study drug discontinuation (if any)
- Death (if any)

At each level of subject summarization, subjects are counted once if they reported at least one TEAE at that level. If a subject reported the same TEAE on multiple occasions, the highest severity (severe > moderate > mild) or study drug relationship (related > probable > possible > unlikely > unrelated) recorded for the event will be summarized. Each summary will be ordered by descending incidence of system organ class and preferred term within each system organ class, based on the Total column.

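### The SAP drops, without declaring it, the summary of TEAEs by action taken that the protocol promises, and the action-taken code list has no entry for a dose decrease

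*Protocol*

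**What the plan says.** **Collection.** Protocol 6.11.4.3 states: "The action taken with regard to study drug in response to each AE will be assessed by the Investigator using the following categories". Four codes follow: no action, interruption, discontinuation and not applicable. The list has no entry for a changed dose and no open category. Protocol 6.11.4.5 requires the field for each AE.

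**Promised analysis.** Protocol 8.6 says that TEAEs by severity, causality, "seriousness and action taken with regard to study drug will be summarized by treatment group". The synopsis says the same.

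**Analysis in the SAP.** SAP 15.2 plans a TEAE overview by severity, seriousness and relationship, followed by tables by system organ class and preferred term. The only table there tied to an action on study drug is "TEAEs leading to study drug discontinuation (if any"). SAP 16.1 lists changes from the protocol, including one to a safety endpoint (the word *confirmed* dropped from the high-bicarbonate criterion). It does not mention action taken.

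**Dose rules.** Under Protocol 5.3, "Dose titrations should be performed on the basis of onsite i-STAT blood bicarbonate measurements only". Appendix 2 provides for an increase at 12 to below 22 mEq/L from Week 4, a decrease at 27 to 30 mEq/L, and a hold at a confirmed value above 30 mEq/L.

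**Route from a laboratory value to an AE.** Under Protocol 6.11.1 an out-of-range result can count as an AE if it is clinically significant in its own right, for example "if some action or intervention or alteration of treatment is required". An isolated fall in bicarbonate or pH is exempt. A rise is not.

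**The concern.** An AE that leads to a hold but not to permanent discontinuation is a basic tolerability result. Protocol 3.2.2 anticipates mainly mild to moderate diarrhea or constipation. In TRCA-101 (Protocol 1.4.1.1) diarrhoea occurred in 20.2% of TRC101 and 12.9% of placebo subjects, and none of it led to discontinuation. A table limited to discontinuation could therefore be nearly empty while temporary holds differed between arms. The protocol foresaw this and asked for the wider summary.

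The second, smaller problem is in the code list. If a high bicarbonate both triggers a dose decrease and is recorded as an AE, the investigator has no code that describes what was done. An event coded as no action, when the dose was in fact lowered, would carry that error into the restored table.

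**Working it through.** **1. Protocol against SAP.**

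| TEAE summary by arm | Protocol 8.6 and synopsis | SAP 15.2 |
|---|---|---|
| Severity | yes | yes |
| Causality | yes | yes |
| Seriousness | yes | yes |
| Action: discontinued | yes | yes |
| Action: interrupted, none, not applicable | yes | absent |

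SAP 16.1 does not declare the last row.

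**2. Does another SAP output supply it?** SAP 13.3 counts subjects with up-titration, down-titration and interruption by arm, with exact intervals, but for any cause. SAP 15.3 and Table 4 count high bicarbonate values. SAP 15.2 lists all AEs by subject. None of these is a by-arm table of TEAEs that led to interruption.

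**3. Where does the missing code matter?** Compare the dose rule, the stated normal range (22 to 29 mEq/L) and the codes:

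| Bicarbonate (mEq/L) | Rule | Out of range? | Accurate code available? |
|---|---|---|---|
| 12 to <22, from Week 4 | increase | yes, low | isolated fall is not an AE |
| 27 to 29 | decrease | no | not an AE by the laboratory route |
| >29 to 30 | decrease | yes, high | none, if judged an AE |
| >30, confirmed | hold | yes, high | yes: interrupted |

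Only the third row lacks a code.

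**4. Illustrative size of the third row.** The documents give no frequency, so it has to be modelled.

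- From SAP 8.2: TRC101 mean changes of 2.00, 2.50, 3.00, 3.50, 3.75 and 4.00 at Weeks 1, 2, 4, 6, 8 and 10; SD 3.0; the stated correlations. Week 12 is left out because no titration is allowed after Week 11.
- Assumed, not in the documents: baseline mean 16.7–18.2, baseline SD 0–1.5, baselines beyond the eligible range of 12 to 20 set to the nearer limit, normal errors, no feedback from dose changes.

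Model: value at visit t = baseline + mean change at t + error at t. The quantity is the proportion of subjects with at least one value above 29 and up to 30.

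One-visit check at Week 10, baseline fixed at 17.3: the mean is 17.3 + 4.00 = 21.3, and Φ((30 − 21.3)/3) − Φ((29 − 21.3)/3) = Φ(2.90) − Φ(2.57) ≈ 0.9981 − 0.9949, or about 0.3%.

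Over the six visits, by simulation:

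| Baseline mean | 16.7 | 17.3 | 17.7 | 18.2 |
|---|---|---|---|---|
| Baseline SD 0 | 0.5% | 1.0% | 1.4% | 2.2% |
| Baseline SD 1.5 | 1.2% | 1.8% | 2.3% | 3.0–3.1% |

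The last cell varies between runs. Leaving baselines unrestricted raises it to 3.6%. In subjects, 0.005 × 120 = 0.6 and 0.031 × 120 = 3.7, so roughly 1–4 of 120. Placebo stays below 0.5% throughout.

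These are upper figures for the coding gap. Not every such reading would be judged an AE, and Appendix 2 blocks a decrease within 14 days of another dose change.

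**The case against.** The best defence of the code list is that it fits the protocol's own rules. Titration rests on i-STAT bicarbonate alone, and nothing provides for lowering the dose in response to an AE. For an ordinary AE the possible responses are to continue, hold or stop, and all three have codes. This stands, except where the AE and the titration trigger are the same measurement.

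The best defence of the SAP is that overshoot and its handling are already reported. SAP 13.3 tabulates dose changes and interruptions by arm, SAP 15.3 tabulates values above 30 mEq/L, and Table 4 adds thresholds above 30 and above 32. SAP 5 also commits to documenting changes from the protocol's planned analyses in the study report. That answers any claim that overshoot is hidden. It does not supply the link from AE to interruption, which concerns any type of event, gastrointestinal ones included.

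A reader might infer more than the documents support:

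- *That a decrease is the protocol's standard dose change.* It is one of two titration directions. The increase applies to every subject below 22 mEq/L from Week 4.
- *That AEs which changed the dose are generally miscoded.* Only the band above 29 and up to 30 mEq/L is affected, and even there AE status depends on the investigator's judgement of clinical significance.
- *That every value of 27 mEq/L or more counts.* The same model puts about 5–16% of TRC101 subjects (6–19 of 120) at or above 27. Most of those values lie within the normal range, and confirmed values above 30 are coded correctly as interruptions.
- *That AE-related interruptions will never be tabulated.* The protocol still calls for the summary. It is the SAP as written that omits it.

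**Conclusion.** The mismatch between protocol and SAP is established from the text alone and needs no assumption. A promised safety summary has been reduced to its discontinuation level without being declared, and no other table shows by arm the TEAEs that led to interruption.

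The coding gap is real but narrow. Its illustrative size, about 0.5–3.1% of TRC101 subjects or roughly 1–4 of 120, rests on SAP 8.2 planning values and an assumed baseline distribution. It is not an observed rate.

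The consequence is limited to safety reporting. The primary and secondary endpoints and the two named safety endpoints (AEs, SAEs and withdrawals due to AE; the high-bicarbonate criterion) are unchanged.

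**What to change.** 1. In SAP 15.2, restore the summary of TEAEs by action taken, by treatment group, with at least a row for study drug interrupted and preferably by system organ class and preferred term. If the sponsor means to drop it, SAP 16 should say so and give the reason.
2. Reconcile the list in Protocol 6.11.4.3 with the titration rules by adding a dose-decreased code, and carry it into the eCRF. No dose-increased code is needed, because an isolated fall in bicarbonate is not reported as an AE. No dosing rule changes.
3. For AEs already entered where a decrease coincided with a recorded AE, query the investigator. Do not recode from dose records alone: they show that the dose changed, not that the AE was the reason. SAP 11.6 already reports 82 + 108 + 27 = 217 randomized subjects, so much of the correction would come through such queries.

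The cost is one table from a field already collected, one code-list entry and a handful of queries.
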